7.7.4 Interim Descriptive Report

An interim descriptive report was prepared 1 year after study start. Within the interim descriptive report, available data on eligible patients regarding the pattern of use of lenalidomide within and outside the EU approved indication, namely the distribution of MDS patients according to predefined categories (eg, transfusion-dependent IPSS low- or int-1-risk MDS with isolated del(5q), or with additional cytogenetic abnormalities, or IPSS risk categories int-2 or high, or patients with MDS without del(5q)) was presented. On 29-Mar-2019, the first interim descriptive report was submitted to the Pharmacovigilance Risk Assessment Committee (PRAC) in order to discuss if the data collected on lenalidomide use, across different groups of MDS patients, are sufficient to allow successful completion of this study. The Assessment Report adopted by the CHMP on 27-Jun-2019 included a request to submit another interim descriptive report in Quarter (Q)1 2020. On 27-Mar-2020, the second interim descriptive report was submitted to PRAC (EMEA/H/C/000717/ANX/041.8). The final Assessment Report, adopted by the CHMP on 10-Dec-2020, concluded that the post-authorisation measure for the second interim report was fulfilled with no further action required.

7.8 Quality Control

See Section 7.6 for the subsection on Study Monitoring and Source Data Verification.

7.9 Limitations of the Research Methods

A drug-utilisation study of lenalidomide in the commercial setting is an important addition to the pharmacovigilance activities for evaluating the safety and use of lenalidomide. This proposed retrospective drug-utilisation study will help determine the extent of use of lenalidomide in MDS by cohort (on-label, off-label, and overall). This will provide valuable information by which to determine the number and type of patients who are being treated outside of the EU approved indication and the consequences of such lenalidomide prescribing vis-à-vis the safety profile of the drug.

To provide a representative analysis of the European population, the study will include information from at least 10 EU countries that have lenalidomide reimbursement for the MDS indication, including data from the EUMDS Registry (de Swart, 2015). More EU countries will potentially be included, once they gain reimbursement for the MDS indication. As data collection for this study is retrospective and relies on existing data sources, there is a significant risk that there will be

missing information. To address this, a common set of variables and other data elements will be defined and will be the same across all sources. This will also facilitate the pooling of aggregated data for analysis. Pooling of raw data is not feasible because raw data will be held by the data owners (ie, data sources in Section 7.4).

Since this study is retrospective and based on secondary data that were collected in several registries, these registries may differ by their initial purpose, the characteristics of their patient populations and availability of some information. The sponsor will define and standardize the criteria for data use both in the aggregated datasets and in the pseudonymized datasets; however, it is expected that a level of inter-registry heterogeneity will exist, which may be a consideration for the meta-analyses. Consequently, the interpretation of results will be made with caution and consider important differences across the original data sources.

Assessing the safety of lenalidomide in a retrospective study will encounter the same lost-to-follow-up issues common to all follow-up studies. A comparison of baseline and treatment characteristics between patients who are and are not lost to follow-up as they were followed in the registry (or other data sources) will enable this form of selection bias to be evaluated where applicable.

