A limitation of the selected EU data sources is that they collect data only from specific countries or patient catchment areas, hence they cannot provide complete representation of the actual real-world European drug-utilisation patterns. However, the EUMDS Registry captures high quality data from 17 EU countries, and it will be used to mitigate this limitation. Of these 17 countries in the selected data sources, results will be included from at least 10 EU countries that have lenalidomide reimbursement for the MDS indication. More EU countries will potentially be included, once they gain reimbursement for the MDS indication. In addition, the Spanish Registry of MDS, the Düsseldorf MDS Registry, the online French Registry of MDS, and the Danish National Acute Leukemia Registry will provide a comprehensive coverage of MDS patients in these four countries to complement the data in the EUMDS Registry. Adjustments will be made for any patients in the four national registries that overlap with patients in the EUMDS Registry.

Operational definition of variables will be consistent regardless of the data source.

To protect privacy and according to the local regulations, analysis of study endpoints will be conducted using aggregated data (majority of analyses) or performed by the local registries (Kaplan-Meier and multivariate analyses). To do the analyses which are based on aggregated data, datasets limited to the necessary variables will be compiled from pseudonymized datasets provided to the sponsor by each registry, and processed in accordance with the applicable regulations regarding privacy protection.

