7.7.3 Safety Analyses

Safety analyses will be based on both the on- and off-label cohorts.

The cumulative incidence of progression to AML will be calculated and stratified according to predictive factors; 95% CIs will be calculated for each of the two cohorts. Aggregated data will be listed by country when possible.

Each registry will be requested to produce Kaplan-Meier curves for on- and off-label patients separately and to calculate the hazard ratio of on- versus off-label patients. They will also be requested to perform multivariate analyses using a Cox model including and on-/off-label indication and prognostic factors as described in the Statistical Analysis Plan on their own individual data. The respective outcomes will be provided by each registry to the study sponsor. Safety for the on- and off-label cohorts will be determined based on the incidence of reported hematological and non-hematological adverse events including SPM other than AML (which is considered as disease progression in patients with MDS). In particular episodes of neutropenia, thrombocytopenia, venous thromboembolic events, infections, bleeding, major cardiac events and SPM will be collected throughout the observational period of a patient in both cohorts as part of the clinical routine.

Due to the secondary use of the data, individual data may not be available. In these conditions, no explorative analyses on confounding or risk factors is foreseen in the protocol, except for progression to AML.

As there is no international standard to define transfusion dependence and there is a risk of error in transfusion coding, an additional sensitivity analysis will be completed to assess the impact of transfusion on the size of the on- and off-label cohorts. This sensitivity analysis will describe the proportion of off-label patients based only on IPSS categories other than low and int-1, and any karyotype other than isolated del(5q).

All safety analyses will be mainly descriptive or explorative in nature.

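### Adverse event, SPM and cohort-level AML cumulative incidence are pooled over registries without registry as a stratum, so on- and off-label figures can differ because of data source

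*Protocol*

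**What the plan says.** Section 7.4 divides the work in two. Kaplan-Meier and multivariate analyses are done by the registries, and most other analyses use aggregated data. Section 7.9 says of the common variable set: "This will also facilitate the pooling of aggregated data for analysis". Raw data are not pooled.

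Section 7.7.3 plans AE and SPM incidence for the on- and off-label cohorts, and AML cumulative incidence with a 95% CI for each cohort. The AML figure is stratified by predictive factors, among which registry is not named. Aggregated data are listed by country where possible. Because individual data may be unavailable, "no explorative analyses on confounding or risk factors is foreseen in the protocol, except for progression to AML". For AML there is a separate within-registry analysis: "Each registry will be requested to produce Kaplan-Meier curves for on- and off-label patients separately and to calculate the hazard ratio", followed by a Cox model on each registry's own data.

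Section 7.9 acknowledges that "these registries may differ by their initial purpose, the characteristics of their patient populations and availability of some information". It states a design measure, "The sponsor will define and standardize the criteria for data use both in the aggregated datasets and in the pseudonymized datasets", but goes on to say that "it is expected that a level of inter-registry heterogeneity will exist, which may be a consideration for the meta-analyses". It then concludes: "Consequently, the interpretation of results will be made with caution and consider important differences across the original data sources".

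Section 7.2.1 defines the on-label cohort as EU patients. The exception admitting patients from the US registry appears in the definitions of the overall population and the off-label cohort, not in that of the on-label cohort.

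**The concern.** A crude cohort figure pooled over sources mixes two things: what happens to patients in that cohort, and which registries supplied them. If registries differ in off-label share and also in how many events occur or are recorded, the two pooled columns can differ when no registry shows any difference. A registry with many off-label patients and poor event capture makes off-label use look safer. One with many off-label patients and thorough capture makes it look more harmful.

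The US registry adds a structural link. As Section 7.2.1 is written, its patients can enter the off-label column but not the on-label one, so label status is partly tied to source by definition.

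The two columns will be read against each other. Section 7.9 says the study should inform the consequences of off-label prescribing for the drug's safety profile.

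**Working it through.** **The plan's own figures.** The off-label share of 230/460 with a Wald interval gives 45.43% to 54.57% (stated 45.4% to 54.6%). AML progression of 39/230 with a Clopper-Pearson interval gives 12.34% to 22.44% (stated 12.3% to 22.4%). Both reproduce. They describe sampling error only and do not bear on this point.

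**Inputs.** The Protocol gives no off-label share, event rate or patient number by registry. All inputs below are assumptions, chosen to show a range.

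**Formula.** Let registry k have n_k patients, off-label share s_k and recorded event risk r_k, with r_k the same for on- and off-label patients.

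- Pooled off-label risk = Σ n_k s_k r_k / Σ n_k s_k
- Pooled on-label risk = Σ n_k (1 − s_k) r_k / Σ n_k (1 − s_k)

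For two registries of equal size, with S = s_1 + s_2, the gap (off minus on) is (r_2 − r_1)(s_2 − s_1) / [S(2 − S)]. It is zero if either the risks or the shares are equal, so both must vary.

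**Two registries of 230, unequal shares.**

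- Shares 80% and 30%, recorded risks 20% and 40%. Off-label: (184 × 0.20 + 69 × 0.40)/253 = 64.4/253 = 25.5%. On-label: (46 × 0.20 + 161 × 0.40)/207 = 73.6/207 = 35.6%. Gap −10.1 points, ratio 0.72.
- Milder: shares 65% and 45%, risks 25% and 35%. Off-label: (149.5 × 0.25 + 103.5 × 0.35)/253 = 73.6/253 = 29.1%. On-label: (80.5 × 0.25 + 126.5 × 0.35)/207 = 64.4/207 = 31.1%. Gap −2.0 points. The 95% half-width is 1.96 × √(0.291 × 0.709/253 + 0.311 × 0.689/207) = 8.4 points, so a bias of this size would be lost in sampling error.

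**Two registries of 230, overall off-label share 50%** (S = 1, so the gap is the product of the two differences; Wald CI with 230 per cohort):

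| Off-label shares | Recorded risks | On-label | Off-label | Gap, points (95% CI) | Ratio |
|---|---|---|---|---|---|
| 50% / 50% | 10% / 24% | 17.0% | 17.0% | 0.0 | 1.00 |
| 40% / 60% | 10% / 24% | 15.6% | 18.4% | 2.8 (−4.1 to 9.7) | 1.18 |
| 20% / 80% | 10% / 24% | 12.8% | 21.2% | 8.4 (1.6 to 15.2) | 1.66 |
| 30% / 70% | 10% / 40% | 19.0% | 31.0% | 12.0 (4.2 to 19.8) | 1.63 |

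**US patients in the off-label cohort only.** Take 230 EU patients per cohort, all with 20% recorded risk.

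- 25 US patients at 30%: (46 + 7.5)/255 = 21.0% against 20.0%, gap 1.0 point.
- 100 US patients at 40%: (46 + 40)/330 = 26.1% against 20.0%, gap 6.1 points.
- 100 US patients at 10%: (46 + 10)/330 = 17.0% against 20.0%, gap −3.0 points.

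In every case a within-registry or registry-stratified difference is 0. That follows from the assumption of no within-registry difference; it is not evidence about the real data.

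**The case against.** The strongest reply is that the on/off-label contrast the Protocol plans in detail is already made within registry. Each registry produces its own Kaplan-Meier curves, hazard ratio and adjusted Cox model for AML, which the Abstract calls the main secondary objective. This stands, and a reader who inferred that the AML comparison as a whole is confounded by registry would be wrong.

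Second, a reader might infer from Section 7.9 that cautious interpretation is the only safeguard. It is not. The Protocol also plans standardised criteria for data use, common operational definitions (Section 7.4), statistical framework documents for data owners (Section 7.7) and listing by country, and it suggests a check of missingness by study setting (Section 7.9). These help, but they neither remove case-mix differences nor create events that a registry never recorded. A country listing is not a registry listing: the EUMDS Registry covers 17 countries and can overlap with the four national registries.

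Third, the Abstract says no formal safety comparison between the cohorts will be made, and the ENCePP checklist says the same of comparisons between groups. This softens the point. It does not dispose of it, because the cohort figures are still shown together for the purpose Section 7.9 describes.

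Fourth, Section 7.9 mentions meta-analyses, and the method may be in the SAP, which is not at hand. Its absence from the Protocol is not counted as a fault.

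Finally, confounding is possible, not shown. Section 7.9 says only that the registries may differ, and no registry-level figure exists to test it. A registry stratum can also remain mixed inside, the EUMDS Registry in particular.

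**Conclusion.** The point holds for AE incidence, SPM incidence and the cohort-level AML cumulative incidence. The last is included because it is not among the analyses assigned to the registries. For these outcomes the Protocol describes pooled results per label cohort, names no registry stratum, and foresees no confounder analysis outside AML. It nevertheless expects heterogeneity to remain after standardisation, and it ties the US source to the off-label cohort by definition.

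A false on/off-label difference can therefore appear if off-label share and event capture both vary by registry. Its size cannot be derived from the Protocol. Under the assumed inputs it runs from nothing, through 2 to 3 points (within sampling error), to 10 to 12 points with strong contrasts, and it can go in either direction. The documents do not support saying that the results are confounded, only that they can be.

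**What to change.** In Section 7.7.3:

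- Show events and patients at risk by registry and label cohort for AEs, SPM and AML cumulative incidence, with US registry patients shown separately.
- Leave a registry that does not record an event out of that event's denominator.
- Present pooled totals as description only.
- If on- and off-label are contrasted, do so within registry or with registry as stratum, for example by Mantel-Haenszel. A registry contributing only one cohort adds nothing to such a contrast.

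In Section 7.9, refer to this display beside the statement on cautious interpretation.

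The cost is wording and a short calculation on counts. For the AE and SPM proportions no individual data are needed beyond what the registries already supply, so the reason Section 7.7.3 gives for not adjusting does not apply. Stratified intervals will be somewhat wider. With six named sources, rare events may be too sparse for a stable stratified estimate, and then the by-registry display alone should stand. Stratifying by registry does not adjust for case mix within a registry, and the report should say so.

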7.10 Other Aspects

Not applicable.

8 PROTECTION OF HUMAN SUBJECTS

In accordance with local regulations, the data sources' owners who will provide the patient records for this study will be asked to confirm that all required regulatory and ethical review requirements on data confidentiality have been completed prior to data use. To protect privacy, data will be pseudonymized by the registries and processed in accordance with local regulations regarding privacy protection.

9 MANAGEMENT AND REPORTING OF ADVERSE EVENTS/ADVERSE REACTIONS

Study MDS-012 is a retrospective drug-utilisation study that is based upon the secondary use of data. Reporting requirements for this non-interventional study are described in Module VI Good Pharmacovigilance Practices, VI.C.1.2.1. Non-interventional Studies. "Real-time" adverse reaction reporting is not required, as described in Good Pharmacovigilance Practices (Module VI) and in the relevant section within Module VIII on the PASS:

• "for non-interventional study designs which are based on secondary use of data, adverse reactions reporting is not required. Reports of adverse events/reactions should only be summarised in the study report, where applicable"

However, as described in the modules for both the Periodic Safety Update Report (PSUR) (Module VII) and the Risk Management Plan (RMP) (Module V), information on collected adverse events will be included in the study report and reported appropriately in both the PSUR and the RMP. In cases of doubt, the reporting requirement will be clarified with the concerned authorities in EU Member States. Information on adverse events other than MDS disease progression, progression to AML, and SPM other than AML, (which is considered as disease progression in patients with MDS), will be collected using the Common Terminology Criteria for Adverse Events (CTCAE) to identify the incidence, but not the severity, of retrospectively identified adverse events. The CTCAE will be used where feasible to provide a common definitional framework for the adverse events collected as part of this study.

10 PLANS FOR DISSEMINATING AND COMMUNICATING STUDY RESULTS

Regular progress report updates as well as final results will be made available to the PRAC as per regulatory requirements via the PSURs. An interim descriptive report was prepared 1 year after study start. On 29-Mar-2019, the first interim descriptive report was submitted to the Pharmacovigilance Risk Assessment Committee (PRAC) in order to discuss if the data collected on lenalidomide use, across different groups of MDS patients, are sufficient to allow successful completion of this study. The Assessment Report adopted by the CHMP on 27-Jun-2019 included a request to submit another interim descriptive report in Quarter (Q)1 2020. On 27-Mar-2020, the second interim descriptive report was submitted to PRAC (EMEA/H/C/000717/ANX/041.8).

The final Assessment Report, adopted by the CHMP on 10-Dec-2020, concluded that the post-approval measure for the second interim report was fulfilled with no further action required.

Final data will be appropriately communicated when available, through presentation at major European and global congresses of hematology and/or oncology. Final results of the MDS drug-utilisation study also will be submitted for expedited review and publication to an appropriate scientific and medical journal.

11 **REFERENCES**

de Swart L, Smith A, Johnston TW, Haase D, Droste J, Fenaux P, et al. Validation of the revised international prognostic scoring system (IPSS-R) in patients with lower-risk myelodysplastic syndromes: a report from the prospective European LeukaemiaNet MDS (EUMDS) registry. Br J Haematol. 2015;170(3):372-83.

ANNEX 1. LIST OF STAND-ALONE DOCUMENTS

None.

ANNEX 2. ENCEPP CHECKLIST FOR STUDY PROTOCOLS

ENCePP Checklist for Study Protocols (Revision 4)

Adopted by the ENCePP Steering Group on 15/10/2018

The European Network of Centres for Pharmacoepidemiology and Pharmacovigilance (ENCePP) welcomes innovative designs and new methods of research. This Checklist has been developed by ENCePP to stimulate consideration of important principles when designing and writing a pharmacoepidemiological or pharmacovigilance study protocol. The Checklist is intended to promote the quality of such studies, not their uniformity. The user is also referred to the ENCePP Guide on Methodological Standards in Pharmacoepidemiology (ENCePP, 2020), which reviews and gives direct electronic access to guidance for research in pharmacoepidemiology and pharmacovigilance.

For each question of the Checklist, the investigator should indicate whether or not it has been addressed in the study protocol. If the answer is "Yes", the section number of the protocol where this issue has been discussed should be specified. It is possible that some questions do not apply to a particular study (for example, in the case of an innovative study design). In this case, the answer 'N/A' (Not Applicable) can be checked and the "Comments" field included for each section should be used to explain why. The "Comments" field can also be used to elaborate on a "No" answer.

This Checklist should be included as an Annex by marketing authorisation holders when submitting the protocol of a non-interventional post-authorisation safety study (PASS) to a regulatory authority (see the Guidance on the format and content of the protocol of non-interventional post-authorisation safety studies [EMA, 2012]). The Checklist is a supporting document and does not replace the format of the protocol for PASS presented in the Guidance and Module VIII of the Good pharmacovigilance practices (GVP) (EMA, 2013).

Study title:

A post-authorisation, non-interventional, retrospective, drug-utilisation study to describe the pattern of use of lenalidomide in patients with myelodysplastic syndromes (MDS)

EU PAS Register[®] number: ENCEPP/EUPAS22604 Study reference number (if applicable): CC-5013-MDS 012, Amendment 3 (Version 2.0)

Secti	on 1: Milestones	Yes	No	N/A	Section Number
1.1	Does the protocol specify timelines for				
	1.1.1 Start of data collectiona	\boxtimes			6
	1.1.2 End of data collection b	\boxtimes			6
	1.1.3 Progress report(s)	\square			6
	1.1.4 Interim report(s)	\square			6
	1.1.5 Registration in the EU PAS Register®			\square	
	1.1.6 Final report of study results.	\square			6

^a Date from which information on the first study is first recorded in the study dataset or, in the case of secondary use of data, the date from which data extraction starts.

^b Date from which the analytical dataset is completely available.

Secti	on 2: R	esearch question	Yes	No	N/A	Section Number
2.1	Does clearl	the formulation of the research question and objectives y explain:	\boxtimes			8
	2.1.1	Why the study is conducted? (eg, to address an important public health concern, a risk identified in the risk management plan, an emerging safety issue)	\boxtimes			8.1
	2.1.2	The objective(s) of the study?	\boxtimes			8.2
	2.1.3	The target population? (ie population or subgroup to whom the study results are intended to be generalised)	\boxtimes			8.1
	2.1.4	Which hypothesis(-es) is (are) to be tested?			\boxtimes	
	2.1.5	If applicable, that there is no a priori hypothesis?			\boxtimes	

Comments:

The study is retrospective and purely descriptive in nature. No formal hypothesis has been formulated

Secti	on 3: Study design	Yes	No	N/A	Section Number
3.1	Is the study design described? (eg, cohort, case-control, cross- sectional, other design)	\boxtimes			9.1.1
3.2	Does the protocol specify whether the study is based on primary, secondary or combined data collection?	\boxtimes			9.1.1
3.3	Does the protocol specify measures of occurrence? (eg,, rate, risk, prevalence)	\boxtimes			9.1.1
3.4	Does the protocol specify measure(s) of association? (eg, risk, odds ratio, excess risk, rate ratio, hazard ratio, risk/rate difference, number needed to harm (NNH))			\boxtimes	
3.5	Does the protocol describe the approach for the collection and reporting of adverse events/adverse reactions? (eg, adverse events that will not be collected in case of primary data collection)				9.3

Secti	on 4: Source and study populations	Yes	No	N/A	Section Number
4.1	Is the source population described?	\square			9.4
4.2	Is the planned study population defined in terms of:				
	4.2.1 Study time period	\square			9.1.2
	4.2.2 Age and sex	\square			9.3
	4.2.3 Country of origin	\square			9.4
	4.2.4 Disease/indication	\square			9.1.1
	4.2.5 Duration of follow-up	\square			9.1.1
4.3	Does the protocol define how the study population will be sampled from the source population? (eg, event or inclusion/exclusion criteria)				9.1.2, 9.2, 9.4

Secti	on 5: Exposure definition and measurement	Yes	No	N/A	Section Number
5.1	Does the protocol describe how the study exposure is defined and measured? (eg, operational details for defining and categorising exposure, measurement of dose and duration of drug exposure)	\boxtimes			9.2
5.2	Does the protocol address the validity of the exposure measurement? (eg, precision, accuracy, use of validation sub- study)			\boxtimes	
5.3	Is exposure categorised according to time windows?			\boxtimes	
5.4	Is intensity of exposure addressed? (eg, dose, duration)			\boxtimes	
5.5	Is exposure categorised based on biological mechanism of action and taking into account the pharmacokinetics and pharmacodynamics of the drug?			\boxtimes	
5.6	Is (are) (an) appropriate comparator(s) identified?			\square	
Comm	ents:				

Secti	on 6: Outcome definition and measurement	Yes	No	N/A	Section Number
6.1	Does the protocol specify the primary and secondary (if applicable) outcome(s) to be investigated?	\boxtimes			8.2
6.2	Does the protocol describe how the outcomes are defined and measured?	\boxtimes			9.3
6.3	Does the protocol address the validity of outcome measurement? (eg, precision, accuracy, sensitivity, specificity, positive predictive value, use of validation sub-study)			\boxtimes	
6.4	Does the protocol describe specific outcomes relevant for Health Technology Assessment? (eg, HRQoL, QALYs, DALYS, health care services utilisation, burden of disease or treatment, compliance, disease management)				

Data will be collected retrospectively and from pre-existing data registries. Data quality is expected to be high, although there could also be areas of missing data due to the real-world setting.

Secti	on 7: Bias	Yes	No	N/A	Section Number
7.1	Does the protocol address ways to measure confounding? (eg, confounding by indication)	\boxtimes			9.9
7.2	Does the protocol address selection bias? (eg, healthy user/adherer bias)	\boxtimes			9.9
7.3	Does the protocol address information bias? (eg, misclassification of exposure and outcomes, time-related bias)	\boxtimes			9.9

Comments:

Secti	on 8: Effect measure modification	Yes	No	N/A	Section Number
8.1	Does the protocol address effect modifiers? (eg, collection of data on known effect modifiers, sub-group analyses, anticipated direction of effect)			\boxtimes	

Section	on 9: Data sources	Yes	No	N/A	Section Number
9.1	Does the protocol describe the data source(s) used in the study for the ascertainment of:				
	9.1.1 Exposure? (eg, pharmacy dispensing, general practice prescribing, claims data, self-report, face-to-face interview)				9.3, 9.4
	9.1.2 Outcomes? (eg, clinical records, laboratory markers or values, claims data, self-report, patient interview including scales and questionnaires, vital statistics)				9.3, 9.4
	9.1.3 Covariates and other characteristics?	\square			9.3, 9.4
9.2	Does the protocol describe the information available from the data source(s) on:				
	9.2.1 Exposure? (eg, date of dispensing, drug quantity, dose, number of days of supply prescription, daily dosage, prescriber)				9.3, 9.4
	9.2.2 Outcomes? (eg, date of occurrence, multiple event, severity measures related to event)	\boxtimes			9.3, 9.4
	9.2.3 Covariates and other characteristics? (eg, age, sex, clinical and drug use history, co-morbidity, co-medications, lifestyle)				9.3, 9.4
9.3	Is a coding system described for:				
	9.3.1 Exposure? (eg, WHO Drug Dictionary, Anatomical Therapeutic Chemical (ATC) Classification System)				9.3, 9.4
	9.3.2 Outcomes? (eg, International Classification of Diseases (ICD), Medical Dictionary for Regulatory Activities (MedDRA))				9.3, 9.4
	9.3.3 Covariates and other characteristics?	\square			9.3, 9.4
9.4	Is a linkage method between data sources described? (eg, based on a unique identifier or other)				9.4

No comparisons are being made between groups. For the Swedish and the Danish databases, reference will be taken from the national patient registries for the endpoint/covariates, and from the dispensing registry for exposure.

Section	on 10: Analysis plan	Yes	No	N/A	Section Number
10.1	Are the statistical methods and the reason for their choice described?	\boxtimes			9.7
10.2	Is study size and/or statistical precision estimated?	\square			9.5
10.3	Are descriptive analyses included?	\square			9.7.1, 9.7.2
10.4	Are stratified analyses included?	\square			9.7.2, 9.7.3
10.5	Does the plan describe methods for analytic control of confounding?				9.7.3
10.6	Does the plan describe methods for analytic control of outcome misclassification?				9.9
10.7	Does the plan describe methods for handling missing data?	\square			9.9
10.8	Are relevant sensitivity analyses described?				9.7.2, 9.7.3
Comm	ents:				

Section	on 11: Data management and quality control	Yes	No	N/A	Section Number
11.1	Does the protocol provide information on data storage? (eg, software and IT environment, database maintenance and anti-fraud protection, archiving)	\boxtimes			9.6
11.2	Are methods of quality assurance described?				9.6, 9.8
11.3	Is there a system in place for independent review of study results?		\boxtimes		

Section 12: Limitations		Yes	No	N/A	Section Number
12.1	Does the protocol discuss the impact on the study results of:				
	12.1.1 Selection bias?	\boxtimes			9.9
	12.1.2 Information bias?	\boxtimes			9.9
	12.1.3 Residual/unmeasured confounding? (eg, anticipated direction and magnitude of such biases, validation sub-study, use of validation and external data, analytical methods).				9.9
12.2	Does the protocol discuss study feasibility? (eg, study size, anticipated exposure uptake, duration of follow-up in a cohort study, patient recruitment, precision of the estimates)				9.5

Section 13: Ethical/data protection issues		Yes	No	N/A	Section Number
13.1	Have requirements of Ethics Committee/ Institutional Review Board been described?	\boxtimes			10
13.2	Has any outcome of an ethical review procedure been addressed?			\boxtimes	
13.3	Have data protection requirements been described?	\boxtimes			10

Comments:

Ethics Committee/Institutional Review Board approvals will be obtained by the selected data sources.

Section 14: Amendments and deviations	Yes	No	N/A	Section Number
14.1 Does the protocol include a section to document amendments and deviations?	\boxtimes			5

Comments:

Section	on 15: Plans for communication of study results	Yes	No	N/A	Section Number
15.1	Are plans described for communicating study results (eg, to regulatory authorities)?	\boxtimes			12
15.2	Are plans described for disseminating study results externally, including publication?	\boxtimes			12

